8.2.1.1 Initial Tumor Imaging

Initial tumor imaging (chest, abdomen, and pelvis) at Screening must be performed within 28 days prior to the date of allocation. The screening images must be submitted to the iCRO for verification of measurable disease per RECIST 1.1 for eligibility before allocation. Tumor imaging performed as part of routine clinical management is acceptable for use as the Screening tumor imaging if it is of diagnostic quality, performed within 28 days prior to the date of allocation, and can be assessed by the iCRO.

Bone imaging will be required for all participants at Screening. Bone imaging are not required to be repeated at Screening if they were performed for standard of care within 42 days prior to allocation and meet protocol requirements.

If brain imaging is required to document the stability of existing metastases, the brain MRI should be acquired during the Screening period.

8.2.1.2 Tumor Imaging During the Study

The first on-study imaging assessment should be performed at 12 weeks ([84 days \pm 7 days]) from the date of allocation. Subsequent tumor imaging should be performed every 6 weeks

(42 days \pm 7 days) or more frequently if clinically indicated. After 54 weeks (378 days \pm 7 days)], participants who remain on treatment will have imaging performed every 12 weeks (84 days \pm 7 days). Imaging timing should follow calendar days and should not be adjusted for delays in cycle starts. Imaging should continue to be performed until disease progression is identified by the investigator, the start of new anticancer treatment, withdrawal of consent, or death, or notification by the Sponsor, whichever occurs first. All supplemental imaging must be submitted to the iCRO.

Objective response should be confirmed by a repeat imaging assessment. Tumor imaging to confirm PR or CR should be performed at least 4 weeks after the first indication of a response is observed. Participants will then return to regular scheduled imaging, starting with the next scheduled imaging time point. Participants who receive additional imaging for confirmation do not need to undergo the next scheduled tumor imaging if it is less than 4 weeks later; tumor imaging may resume at the subsequent scheduled imaging time point. Note: Response does not typically need to be verified in real time by the BICR.

On-study brain or bone imaging should be performed if clinically indicated or to confirm CR (if other lesions indicate CR and brain or bone lesions existed at baseline).

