4 STUDY DESIGN

4.1 Overall Design

This is a Phase 2, nonrandomized, single-arm, multisite, open-label study of pembrolizumab + lenvatinib in participants with previously untreated advanced/metastatic nccRCC including all IMDC risk groups. Participants must have histologically confirmed diagnosis of nccRCC pathology to participate. Collecting duct histology is excluded.

Approximately 152 participants will be enrolled and allocated to receive treatment with pembrolizumab 400 mg Q6W and lenvatinib 20 mg QD. Pembrolizumab treatment will continue for up to ~2 years or until a discontinuation criterion (Section 7.1) is met, and lenvatinib treatment may continue beyond 2 years until a discontinuation criterion (Section 7.1) is met.

During initial treatment, participants who have been receiving study intervention for ≥ 24 weeks (at least 4 cycles) and who attain a CR may consider stopping pembrolizumab treatment. If a confirmed CR per RECIST 1.1 is attained after at least 24 weeks, participants must receive pembrolizumab for at least 1 additional cycle after CR is first documented.

Treatment may continue after radiographic progression of RCC per RECIST 1.1 as long as the investigator believes that the participant is still receiving clinical benefit from study intervention and that the potential benefit of continuing study intervention outweighs potential risks. Treatment beyond disease progression requires Sponsor consultation. Continued participation requires additional consent (Section 8.1.1). Participants who continue treatment beyond disease progression will continue with all protocol-required assessments and procedures, and will resume the existing imaging schedule.

Participants who stop pembrolizumab treatment after receiving 18 administrations (2 years) of pembrolizumab with SD or better, or participants who have been receiving pembrolizumab for at least 24 weeks, attain a confirmed CR, and stop pembrolizumab may be eligible for up to 9 additional cycles (approximately 1 year) of pembrolizumab upon experiencing investigator-assessed PD. This retreatment is termed the Second Course Treatment Phase and is only available if the study remains open and the participant meets the criteria in Section 6.6.5. Participants may also continue lenvatinib treatment during the Second Course Treatment Phase. If lenvatinib is continued, participants will be treated at the same dose level and frequency of lenvatinib they were receiving when PD occurred.

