Imaging assessments will include chest CT and abdomen and pelvis CT/MRI throughout the study. Bone scans will be performed at screening and will only be repeated throughout the study if a participant has a positive result at screening. Brain imaging at screening is only required for participants with previously documented brain metastases. On-study brain imaging will only be performed as clinically indicated or to confirm CR in a participant with brain lesions at baseline. All imaging obtained will be submitted to the iCRO for BICR, which will assess the images per RECIST 1.1, adjusted to allow for a maximum of 10 total target lesions and a maximum of 5 target lesions per organ. However, all decisions to

discontinue study intervention(s) due to disease progression are based solely on the site radiology's assessment.

Adverse event monitoring will be ongoing throughout the study. AEs will be graded in severity according to the guidelines outlined in the NCI CTCAE Version 5.0.

During both Initial Treatment Phase and the Second Course Treatment Phase, if pembrolizumab is discontinued because of toxicity, lenvatinib alone may be continued based on physician discretion regarding the benefits of continuing VEGFR-based oral monotherapy. If lenvatinib is discontinued due to toxicity, pembrolizumab alone may be continued.

Specific procedures to be performed during the study, as well as their prescribed times and associated visit windows, are outlined in the SoA in Section 1.3. Details of each procedure are provided in Section 8.

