8.2.1.3 End-of-Treatment and Follow-up Tumor Imaging

For participants who discontinue study intervention, tumor imaging should be performed at the time of treatment discontinuation (\pm 4 week window). If previous imaging was obtained within 4 weeks prior to the date of discontinuation, then imaging at treatment discontinuation is not mandatory. For participants who discontinue study intervention due to documented disease progression, this is the final required tumor imaging.

For participants who discontinue study intervention without documented disease progression, every effort should be made to continue monitoring disease status by tumor imaging using the same imaging schedule used while on treatment calculated from the date of allocation (see Section 8.2.1.2) until the start of a new anticancer treatment, disease progression, pregnancy, death, withdrawal of consent, or the end of the study, whichever occurs first.

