9.6.1.2 Duration of Response

If sample size permits, DOR will be summarized descriptively using Kaplan-Meier medians and quartiles. Only the subset of participants who show a confirmed CR or PR will be included in this analysis. Censoring rules for DOR are summarized in [Table 10](#).

For each DOR analysis, a corresponding summary of the reasons responding participants are censored will also be provided. Responding participants who are alive, have not progressed, have not initiated new anticancer treatment, have not been determined to be lost to follow-up, and have had a disease assessment within ~5 months of the data cutoff date are considered

ongoing responders at the time of analysis. If a participant meets multiple criteria for censoring, the censoring criterion that occurs earliest will be applied.

Table 10 Censoring Rules for Duration of Response

Situation	Date of Progression or Censoring	Outcome
No progression nor death, no new anticancer therapy initiated	Last adequate disease assessment	Censor (non-event)
No progression nor death, new anticancer therapy initiated	Last adequate disease assessment before new anticancer therapy initiated	Censor (non-event)
Death or progression immediately after ≥ 2 consecutive missed disease assessments or after new anticancer therapy, if any	Earlier date of last adequate disease assessment prior to ≥ 2 missed adequate disease assessments and new anticancer therapy, if any	Censor (non-event)
Death or progression after ≤ 1 missed disease assessments and before new anticancer therapy, if any	PD or death	End of response (Event)
PD=progressive disease. A missed disease assessment includes any assessment that is not obtained or is considered inadequate for evaluation of response.		

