9.6.1.3 Progression-free Survival

The nonparametric Kaplan-Meier method will be used to estimate the PFS curve.

Since disease progression is assessed periodically, PD can occur any time in the time interval between the last assessment where PD was not documented and the assessment when PD is documented. The true date of disease progression will be approximated by the earlier of the date of the first assessment at which PD is objectively documented per RECIST 1.1 by BICR and the date of death. Death is always considered a PD event.

For the primary analysis, any participant who experiences an event (PD or death) immediately after 2 or more missed disease assessments will be censored at the last disease assessment prior to the missed visits. In addition, any participant who initiates new anticancer therapy prior to documented progression will be censored at the last disease assessment prior to the initiation of new anticancer therapy. Participants who do not start new anticancer therapy and who do not experience an event will be censored at the last disease assessment. If a participant meets multiple criteria for censoring, the censoring criterion that occurs earliest will be applied. Sensitivity analyses will be performed for PFS based on investigator's assessment.

In order to evaluate the robustness of the PFS endpoint per RECIST 1.1 by BICR, 2 sensitivity analyses with different sets of censoring rules will be performed. The first sensitivity analysis follows the intention-to-treat principle. That is, PDs/deaths are counted as events regardless of missed study visits or initiation of new anticancer therapy. The second

sensitivity analysis considers initiation of new anticancer treatment or discontinuation of treatment due to reasons other than CR, whichever occurs later, to be a PD event for participants without documented PD or death. If a participant meets multiple criteria for censoring, the censoring criterion that occurs earliest will be applied. The censoring rules for the primary and sensitivity analyses are summarized in [Table 11](#).

Table 11 Censoring Rules for Primary and Sensitivity Analysis of PFS

Situation	Primary Analysis	Sensitivity Analysis 1	Sensitivity Analysis 2
PD or death documented after ≤ 1 missed disease assessment, and before new anticancer therapy, if any	Progressed at date of documented PD or death	Progressed at date of documented PD or death	Progressed at date of documented PD or death

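### Scans stop at site-called progression while DOR and PFS count only central-review progression or death; the censoring rules can then drop later deaths, and DOR has no alternative estimate

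*Combined protocol and SAP*

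**What the plan says.** **Imaging.** Section 8.2.1.2 sets the stopping point for scans: "Imaging should continue to be performed until disease progression is identified by the investigator", with new therapy, consent withdrawal, death or Sponsor notification as the other stopping points. Section 8.2.1.3 adds, of the scan at treatment discontinuation: "For participants who discontinue study intervention due to documented disease progression, this is the final required tumor imaging". Under Section 4.1, decisions to "discontinue study intervention(s) due to disease progression are based solely on the site" radiology reading. No real-time BICR check of progression is described. There is one exception: participants treated beyond progression, after Sponsor consultation and further consent, "will resume the existing imaging schedule" (Section 4.1), and their scans go to the imaging CRO (Section 8.2.1.5).

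**Endpoints.** Section 9.4.1 and Table 12 base PFS and DOR on BICR progression or death.

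**Censoring.** In the primary PFS analysis, "any participant who experiences an event (PD or death) immediately after 2 or more missed disease assessments will be censored" (Section 9.6.1.3, Table 11). Table 10 applies the same rule to DOR. Both tables also censor events that follow new anticancer therapy. The footnote to Table 10 reads: "A missed disease assessment includes any assessment that is not obtained or is considered inadequate for evaluation of response". Table 11 has no such footnote. The paragraph of Section 9.6.1.3 just before the censoring rule says: "Death is always considered a PD event". Separately, participants who have an extra confirmatory scan "do not need to undergo the next scheduled tumor imaging if it is less than 4 weeks later" (Section 8.2.1.2).

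**Checks.** PFS has three: investigator-assessed PFS, Sensitivity Analysis 1 (events count despite missed visits or new therapy) and Sensitivity Analysis 2 (certain treatment stops or new therapy count as progression when neither progression nor death is documented). DOR has one rule set and a summary of censoring reasons.

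**The concern.** The reader who ends imaging is not the reader whose progression date counts. When the two disagree, the protocol can remove the scans on which BICR might later have agreed. The absence of those scans can then turn a later death from an event into a censored observation. The participants concerned are those the site thought were progressing, so they probably have a higher hazard than those still at risk, and Kaplan-Meier assumes the opposite.

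The trial has a single arm, so no comparator shares the distortion. Median DOR and PFS will be read at face value beside the ORR. For PFS a reader can turn to the investigator-assessed analysis; for DOR there is nothing to turn to.

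**Working it through.** **1. The plan's own figures.** The only design calculation is Table 13 (exact 95% limits for ORR, n = 152). With lower limit Beta⁻¹(0.025; x, n−x+1) and upper limit Beta⁻¹(0.975; x+1, n−x), all four rows reproduce to one decimal, for example x = 64: 42.1% (34.2, 50.4). No figure is given for DOR or PFS, so the rest is a reading of the rules followed by an illustration.

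**2. The rules applied to one participant.** Scans fall at Week 12, every 6 weeks to Week 54, then every 12 weeks. Suppose the site calls progression, BICR does not, treatment stops and no new therapy starts.
- Last scan Week 30: scans would have fallen at Weeks 36 and 42. Death at Week 40 follows one unobtained scan and counts. Death at Week 44 follows two and is censored at Week 30. The threshold is 42 − 30 = 12 weeks.
- Last scan Week 66: the next two dates are Weeks 78 and 90. The threshold is 90 − 66 = 24 weeks.
- If new therapy starts before death, the death is censored whatever the scan count.

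**3. The waived scan.** Response at Week 12, extra confirmatory scan at Week 16: the Week 18 scan is 2 weeks later and is waived. Under the Table 10 footnote it was not obtained, so one truly missed scan at Week 24 makes two in a row. This can happen only to confirmed responders, who are the DOR population.

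**4. Illustrative size for PFS.** Simulation on the scan calendar, 300,000 participants per scenario. Apart from the 9.2 months, which Section 2.1.3 reports for lenvatinib plus everolimus, the inputs are assumptions outside the documents:
- median time to site progression 9.2 or 14 months;
- 0% to 30% of site progressions not called by BICR on that scan, with mean lag to BICR progression 3 months;
- median survival 12 months after site progression;
- 30% or 60% starting new therapy 2 to 8 weeks after progression;
- cutoff at 36 to 54 months;
- nobody scanned after site progression.

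The comparator is scanning continued to BICR progression with every progression and death counted.

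| Discordance | 12-month PFS, median 9.2: planned vs comparator | Shift (points) | 12-month PFS, median 14: planned vs comparator | Shift (points) |
|---|---|---|---|---|
| 0% | 0.434 vs 0.434 | 0 | 0.579–0.581 vs 0.579–0.581 | 0 |
| 10% | 0.471 vs 0.448 | +2 | 0.608–0.610 vs 0.588–0.590 | +2 |
| 20% | 0.51 vs 0.46 | +5 | 0.640–0.641 vs 0.599–0.600 | +4 |
| 30% | 0.55 vs 0.47 | +8 | 0.673 vs 0.607–0.610 | +6 to +7 |

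If scans continued but censoring at new therapy stayed, the shifts would be about 1–2, 2–3.5 and 3–6 points at 10%, 20% and 30%. Among discordant participants, 12–17% had a death that counted, 22–43% had a death removed by the missed-scan rule alone, and 28–56% were censored for new therapy.

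**5. Do the PFS checks reveal it?** At 20% discordance, median 9.2 months and 60% starting new therapy, 12-month PFS was:
- planned primary 0.511;
- Sensitivity Analysis 1, 0.512;
- Sensitivity Analysis 2, 0.504;
- comparator 0.461;
- investigator-assessed 0.435.

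Sensitivity Analysis 1 restores deaths, but at the death date. Under Table 11, Sensitivity Analysis 2 also uses the death date for anyone who dies. Only the investigator-assessed analysis moves clearly. In this run it and the primary analysis lie on either side of the comparator.

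**6. DOR.** DOR was not simulated against that comparator. A separate run on the same calendar assumed median DOR 9.9 or 18 months, median survival after progression 6 or 12 months, and 0% or 50% starting new therapy after one month. Twelve-month DOR rose about 2–3, 4–6 and 6–10 points at 10%, 20% and 30% discordance. Those rises are relative to no discordance, so part of them is genuine reader difference rather than bias.

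**The case against.** - **Imaging does not stop for everyone.** Participants treated beyond progression stay on the scan schedule, and a discontinuation scan is due unless one was done in the previous 4 weeks. This stands. A reader might infer that BICR progression can never be recorded after a site call; the documents do not support that.
- **PFS is already checked three ways.** This stands, and investigator-assessed PFS avoids the problem. DOR has no counterpart.
- **A scan that is no longer required need not be a missed scan.** This is a fair reading for PFS, since the definition sits under Table 10 only. For DOR the footnote covers any assessment not obtained and makes no exception. The text needs clarifying in either case.
- **The sentence on deaths concerns the dating of events, and its exceptions follow at once.** This is largely right. The two still disagree as written, but only wording is at stake.
- **The waived scan is marginal.** One waived scan cannot trigger censoring. On the 6-week schedule the next regular scan can itself confirm response, so an extra scan is often unnecessary. No frequency is given.
- **New therapy is a separate and often larger route.** This stands. Redefining a missed scan would not restore those deaths.
- **Bias is not shown.** This stands. A reader might infer that both endpoints are overstated, or that medians inflate by 1/(1−f): 1.11, 1.25 and 1.43 for f = 10%, 20% and 30%. That formula assumes no discordant death counts, whereas 12–17% of discordant participants had one that did. It also takes site progression as truth, although the endpoint is BICR progression. It is at best a ceiling.

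**Conclusion.** The point holds as a risk of upward bias in BICR DOR and BICR PFS, not as a demonstrated overstatement. It needs two conditions: site progression that BICR does not call on the same scan, and a higher later risk in those participants. The documents give no discordance rate. With full agreement the shift is zero; at an assumed 10% to 30%, 12-month PFS moves by about 2 to 8 points under the assumptions listed. Deaths after at most one missed scan and before new therapy still count.

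The gap that matters most is DOR, where no alternative estimate is planned. ORR uses none of these censoring rules and is unaffected. Severity is moderate, because both endpoints are secondary and descriptive in a study with no hypothesis test.

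**What to change.** 1. In Section 9.6.1.2, or in the supplemental SAP before final database lock, prespecify two DOR sensitivity analyses. One counts investigator progression without BICR progression as an event at the investigator's date. The other counts deaths regardless of missed scans or new therapy. The first is likely to be the more informative, since restoring deaths alone barely moved 12-month PFS. For both DOR and PFS, report how many participants were censored after investigator progression without BICR progression.
2. Give Tables 10 and 11 one shared definition under which scans no longer required after investigator progression, or waived after a confirmatory scan, are not missed.
3. Qualify the sentence on deaths in Section 9.6.1.3 so that it agrees with the primary censoring rule.

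The cost is wording plus one extra table, using investigator progression dates that the planned investigator-assessed PFS already needs. The supportive medians may be shorter.

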8.2.1.3 End-of-Treatment and Follow-up Tumor Imaging

For participants who discontinue study intervention, tumor imaging should be performed at the time of treatment discontinuation (\pm 4 week window). If previous imaging was obtained within 4 weeks prior to the date of discontinuation, then imaging at treatment discontinuation is not mandatory. For participants who discontinue study intervention due to documented disease progression, this is the final required tumor imaging.

For participants who discontinue study intervention without documented disease progression, every effort should be made to continue monitoring disease status by tumor imaging using the same imaging schedule used while on treatment calculated from the date of allocation (see Section 8.2.1.2) until the start of a new anticancer treatment, disease progression, pregnancy, death, withdrawal of consent, or the end of the study, whichever occurs first.

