8.10.4 Posttreatment Visits

8.10.4.1 Safety Follow-up Visit

The mandatory Safety Follow-up Visit should be conducted approximately 30 days after the last dose of study intervention or before the initiation of a new anticancer treatment, whichever comes first.

Participants who are eligible for retreatment/crossover with pembrolizumab may have up to 2 safety follow-up visits, 1 after the Initial Treatment Phase and 1 after the Second Course Treatment Phase.

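### The end-of-treatment scan may fall after new anticancer therapy has started, and the primary PFS and DOR rules then censor a progression it shows

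*Combined protocol and SAP*

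**What the plan says.** Section 8.2.1.3 governs the scan at the end of treatment: "tumor imaging should be performed at the time of treatment discontinuation". The window is 4 weeks before or after discontinuation, and the scan is waived if one was taken in the preceding 4 weeks. The visible text sets no order between this scan and the start of another anticancer therapy.

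Routine imaging stops at a switch. Section 8.2.1.2 reads "Imaging should continue to be performed until disease progression is identified by the investigator, the start of new anticancer treatment", among other stopping events, and 8.2.1.3 stops follow-up imaging at the same point.

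For primary PFS, 9.6.1.3 states that "any participant who initiates new anticancer therapy prior to documented progression will be censored at the last disease assessment prior to the initiation" of that therapy. Table 11 applies the same treatment to a progression or death that comes after new therapy. For DOR, Table 10 gives the censoring date for participants who switch without an event as "Last adequate disease assessment before new anticancer therapy initiated", and it also censors a progression or death after new therapy.

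Table 11 defines two PFS sensitivity analyses. Both count a progression or death documented after new therapy as an event on its date. No counterpart is given for DOR.

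The protocol does set an order elsewhere. Under 8.10.4.1 the Safety Follow-up Visit takes place about 30 days after the last dose "or before the initiation of a new anticancer treatment, whichever comes first".

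**The concern.** The imaging window and the censoring rules interact. Suppose a participant stops for clinical deterioration, starts another therapy 2 weeks later and has the end-of-treatment scan at week 4. The site has complied with 8.2.1.3. If BICR reads progression on that scan, primary PFS and DOR discard it and censor the participant at the last scan before the switch. A later death is discarded as well.

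This censoring is informative, because these participants are being switched when their disease has just worsened. Dropping their events pushes the Kaplan-Meier curve up. The trial is single-arm, so there is no comparator in which the distortion could cancel.

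The scan schedule leaves room for it. The first on-study scan is at Week 12 and scans are 12 weeks apart after Week 54, so a deteriorating participant may have no scan in the 4 weeks before stopping. Someone who stops before Week 12 and switches before the scan has only the baseline image and is censored at time zero for PFS.

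**Working it through.** **The plan's own figure.** The plan gives no PFS or DOR assumption and no precision for either. Its only design calculation is Table 13 (Clopper-Pearson limits for ORR, 152 participants). All four rows reproduce, for example 53/152 = 34.9% (27.3, 43.0). The table does not bear on this point.

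**Who is exposed.** A participant must have no earlier BICR-documented progression, no scan in the previous 4 weeks that already shows it, and new therapy begun before the end-of-treatment scan. Call this share of participants q. The documents do not give it.

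**Simulation inputs.**
- From the protocol: scans at Week 12, every 6 weeks to Week 54, then every 12 weeks; final analysis about 36 months after last enrolment.
- Assumed: exponential PFS with true median 9, 12 or 18 months; follow-up uniform on 36 to 54 months; q of 2%, 5%, 10% or 20% (about 3, 8, 15 or 30 of 152), unrelated to the time of progression; end-of-treatment scan 0 to 4 weeks after progression.
- 200,000 participants per scenario. The reference counts the end-of-treatment progression on its date. The primary rule censors at the previous scan.

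**Week-54 PFS, reference to primary rule:**

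| q | median 9 mo | median 12 mo | median 18 mo | rise (points) |
|---|---|---|---|---|
| 2% | 38.5 to 39.2 | 48.8 to 49.5 | 61.9 to 62.5 | 0.6–0.7 |
| 5% | 38.3 to 40.1 | 48.8 to 50.5 | 62.1 to 63.5 | 1.4–1.8 |
| 10% | 38.5 to 42.2 | 48.7 to 52.2 | 61.8 to 64.8 | 3.0–3.7 |
| 20% | 38.4 to 46.0 | 48.8 to 56.0 | 61.9 to 68.0 | 6.1–7.6 |

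A separate run with a 9.2-month median (the protocol's lenvatinib plus everolimus figure, n=31) moved 12-month PFS from about 43% to 45%, 47% and 51% at q of 5%, 10% and 20%.

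**Check by hand.** Censoring a share q of events at about the time they occur leaves a hazard of (1 − q) times the true one, so the curve estimates approximately S^(1 − q). With S = 0.488: 0.488^0.95 = 0.506, 0.488^0.90 = 0.524, 0.488^0.80 = 0.563. The simulation gave 0.505, 0.522 and 0.560.

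**Scale.** The 95% half-width of a proportion near 50% with 152 participants, ignoring censoring, is 1.96 × √(0.5 × 0.5 / 152) = 0.0795, about 8 points.

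**Censored at time zero.** Week 12 is 12/4.345 = 2.76 months. With a 9.2-month median, 1 − 0.5^(2.76/9.2) = 0.188 progress before it. Then 152 × 0.188 × q gives 1.4, 2.9 and 5.7 participants at q of 5%, 10% and 20%. They have no on-study response and do not enter DOR.

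**Medians.** With a true median of 9 months, the Kaplan-Meier median is 9.7 months at q = 5% (no change), 11.0 at 10% and 12.4 at 20%. These are Weeks 42, 48 and 54 divided by 4.345, so the jumps are steps between scan dates. The survival percentages describe the shift better.

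**Sensitivity analyses.** Under PFS Sensitivity Analysis 1 the late scan counts on its own date, so the shift is zero by construction. DOR was not simulated.

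**The case against.** The strongest reply is that the plan already handles this for PFS. Both sensitivity analyses in Table 11 count a progression or death after new therapy. Sensitivity Analysis 2 also treats the switch itself as an event when neither is documented. A reader might infer from the primary rule that these progressions are lost to every PFS analysis, and Table 11 shows that they are not. Three things remain exposed:
- the headline PFS estimate;
- DOR;
- Sensitivity Analysis 1 when the scan is skipped because the participant has switched and no death follows.

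A second reply is that the exposed group may be small. The instruction is to scan at discontinuation, with the 4 weeks as a tolerance. Extra scans are allowed when clinically indicated, and unscheduled scans showing progression go to central review. This stands. Nothing in the documents supports a share of 10% or 20% over one of 2%.

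Third, the notes to the imaging row of Table 1 are unreadable in the copy available, so an instruction there cannot be ruled out.

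Fourth, PFS and DOR are secondary and descriptive, with no hypothesis test. Missing data count as nonresponse for ORR, which these censoring rules do not touch. This limits the importance of the point without removing it.

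**Conclusion.** The point holds in conditional form. A scan that complies with the protocol can show a progression that neither primary PFS nor DOR counts, and when that happens the bias is upward. At a 5% share the rise is under 2 points of week-54 PFS in the main simulation, small against a half-width of about 8. At 10% to 20% it is roughly 3 to 8 points and would matter to a reader of the PFS curve. These figures rest on assumed medians and an assumed share. No size is available for DOR.

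Two stronger readings are not supported. One is that PFS and DOR are biased upward as a matter of course: this needs a known share of early switchers, which the documents do not provide. The other is that median PFS would be inflated by more than a month: that reflects the scan grid and needs an assumed share well above 5% in the 9-month scenario.

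This is a cheap improvement to two secondary endpoints and does not threaten the primary result.

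**What to change.** 1. First check that the imaging-row notes of Table 1 do not already set the order. If they do not, state in 8.2.1.3 that the discontinuation scan is to be obtained within the existing window and, where feasible, before new anticancer therapy starts. The qualifier is needed because 8.2.1.5 recognises progression that calls for urgent alternative intervention. The sentence concerns the date of the scan and leaves treatment decisions alone.
2. Report the number of discontinuation scans taken after new therapy began. The protocol is at Amendment 04 and its summary of changes says interim analyses have been performed, so retiming scans cannot repair data already collected. This count would show whether the problem is real here.
3. Add a DOR sensitivity analysis that counts progression or death regardless of new anticancer therapy, parallel to PFS Sensitivity Analysis 1.

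The cost is one sentence, one count and one extra analysis, plus minor scheduling effort for participants who switch quickly. No procedure is added.
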